Topical Capsaicin Cream for Treatment of Suspected Cyclical Vomiting Syndromes

NCT03223350

Date: April 5, 2017

Study Design and Setting

This randomized, double-blind, placebo-controlled pilot trial was performed at an urban academic trauma center hospital with 100,000 annual ED visits. The study was approved by the institutional review board and registered with the National Library of Medicine (NCT03223350). Research team members screened patients using the electronic medical record system. We obtained written informed consent from all participants. Patients were enrolled between December 2017 and July 2019.

All adult patients (age ≥ 18 years) presenting with a suspected exacerbation of CHS and had active vomiting or nausea in the ED were eligible. Exclusion criteria were: minors (< 18 years old), pregnancy, known allergy to capsaicin or hot peppers, those with resolution of nausea prior to randomization, outpatient use of prescription antiemetics within the past 24- hours, acute infectious or surgical abdominal conditions, and inability to provide informed consent. The original protocol excluded patients that received any antiemetic medication in the ED prior to enrollment. Half-way through the trial, we made a protocol change that removed this exclusion criteria and allowed enrollment of patients that received an antiemetic medication in the ED prior to randomization as long as nausea was still present. We made this protocol change due to the difficulty obtaining consent and enrolling symptomatic patients prior to receiving standard antiemetic therapy.

Interventions, Randomization, and Blinding

Research team members assessed eligibility among all patients who presented with suspected CHS. Any potentially eligible female patients of childbearing age had to have a pregnancy test performed prior to enrollment. We randomized patients that provided informed consent to the experimental or control group using REDCap database (Research Electronic Data Capture, Vanderbilt University). Randomization used 1:1 allocation and stratified by gender. The treatment consisted of five grams of topical 0.1% capsaicin cream, and the placebo consisted of a moisturizing cream. The study team pre-packaged the capsaicin and placebo creams in identical single-dispensing tubes and coded each with a study identification number. The capsaicin cream and the placebo were identical in appearance and had no scent. An ED nurse applied study medication cream once to the abdomen in a uniform manner. The treating physicians, research team members, and patients were blinded to study drug allocation. In addition to study medication, patients received conventional therapy, which was determined by the treating physician independent of study enrollment.

Methods and Measurements

Research team members collected relevant patient demographic, clinical, and treatment data and entered data into a secure REDCap. We measured the intensity of the patient's nausea upon randomization and at 30- and 60-minutes following application of study medication. For nausea assessment, we used a previously validated visual analog scale (VAS) that ranged from 0 to 10 cm (10 being most severe).^{18,19} A research team member remained at the patient's bedside for the first 60 minutes to assess for any immediate adverse events. Additionally, the patient was assessed for any adverse events over the entire course of the patient's ED stay and, later, through a phone call at 30 days.

Outcomes

The primary outcome was the patient's reported nausea on the VAS at 30 minutes following study medication application. Secondary outcomes were the patient's reported nausea and percent change from baseline at 60 minutes, disposition status (hospital admission or discharge), and the need for rescue anti-emetic medication. The 30- and 60-minutes outcome assessment times were based on clinical experience that capsaicin has a rapid effect (<30 minutes) but may have a delayed maximum effect. Hospital admission included placement on observation or inpatient units.

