## **Statistical Analysis Plan**

Assuming a clinically meaningful effect size of 3 cm difference in the nausea VAS (primary outcome) between capsaicin and placebo groups and standard deviation of 2.5 cm, we estimate that we would require 12 subjects in each of two groups to allow for 80% power and alpha 0.05. To account for imprecision in the effect size and the unknown factor of early treatment withdrawal due to skin irritation, we planned a total sample size of 30 participants.

We evaluated baseline characteristics of the overall cohort using descriptive statistics and report discrete data as frequencies and percentages and continuous data as medians and interquartile ranges. For all outcomes, we used intention-to-treat analysis. For one patient in the capsaicin group, the nausea VAS at 30 and 60 minutes was missing; we used multiple imputation to assign these values. Analysis included Chi-square test or Fisher's exact test for unadjusted comparisons of categorical outcomes between treatment groups. Analysis also included student's t-test, or Mann-Whitney U test, as appropriate for unadjusted comparisons of continuous variables between treatment groups. A p-value <0.05 (two-tailed) was considered statistically significant for all tests. We performed all analyses using SAS 9.4 (Cary, NC) and report primary results with 95% confidence intervals (CI).

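### Patients given an ED antiemetic before randomization were admitted from half-way, and the 30-minute comparison neither reports nor adjusts for it: a loss of precision and clarity, not a bias

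*Protocol*

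**What the plan says.** The eligibility paragraph of the Protocol (Study Design and Setting) states that patients given any ED antiemetic before enrollment were at first excluded. Half-way through, this was reversed: the amended rule "allowed enrollment of patients that received an antiemetic medication in the ED prior to randomization as long as nausea was still present". The reason given is practical, namely that symptomatic patients were hard to consent and enroll before standard treatment had started. No drug, dose or minimum interval since the antiemetic is stated. Neither is the number of patients enrolled before and after the change. The same paragraph still lists as an exclusion "outpatient use of prescription antiemetics within the past 24- hours".

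On allocation, the Protocol (Interventions, Randomization, and Blinding) says "Randomization used 1:1 allocation and stratified by gender". Both arms also received conventional therapy chosen by the treating physician.

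The primary outcome is the VAS score itself at 30 minutes (Protocol, Outcomes). The SAP analyses it by t-test or Mann-Whitney test, described as "unadjusted comparisons of continuous variables between treatment groups". The available SAP text names no covariate, no subgroup and no display by prior ED antiemetic or by period before and after the change.

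**The concern.** Under the first rule, every patient entered without an ED antiemetic on board. Under the second, persisting nausea after an ED antiemetic became a way into the trial. Such patients are selected for incomplete response, and some may still be responding to the earlier dose when the 30-minute reading is taken. Prior ED antiemetic is therefore a plausible predictor of the primary outcome. It is known before randomization, yet it is neither balanced by design nor used in the analysis.

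Two things are at stake. One is precision: with about 30 patients, an unadjusted predictor of this kind adds noise to the difference between arms. The other is interpretation: if capsaicin's effect differs by prior antiemetic, the pooled estimate depends on a mix that the documents do not report.

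The two eligibility rules also sit awkwardly together. A prescription antiemetic taken at home 23 hours earlier excludes a patient, while one given in the ED shortly before randomization does not. No reason for the difference is given.

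**Working it through.** **Inputs from the documents.** The target difference is 3 cm, with "standard deviation of 2.5 cm" and "80% power and alpha 0.05"; tests are two-sided ("A p-value <0.05 (two-tailed) was considered statistically significant for all tests"). The planned total is 30, taken as 15 per arm.

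**Assumptions, not in the documents.** K patients of 30 are pre-treated, with K from 8 to 15. If half-way means half of enrollment, 15 is the ceiling, because it needs every later patient to be pre-treated. Prior antiemetic shifts the 30-minute VAS by d = 1, 2 or 3 cm.

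**1. The plan's own figure.** The standardized effect is 3 / 2.5 = 1.2. A two-sided two-sample t-test at 0.05 with 80% power needs 11.94, so 12 per group, as the SAP states (power 0.802). At 15 per arm, power is 0.887.

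**2. Bias and type I error.** The antiemetic is given before allocation, so its expected effect is the same in both arms. In null simulations of 40,000 trials per setting, with K = 8 or 15 and d = 0, 2 or 3 cm, the mean difference between arms was within 0.01 cm of zero. Type I error was 4.8% to 5.2%.

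**3. Added variance.** With p = K/30, SD = sqrt(2.5² + p(1 − p)d²). For K = 15, p(1 − p) = 0.25; for K = 8, it is 0.267 × 0.733 = 0.196.

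| Shift d | SD, K = 8 | Power, K = 8 | SD, K = 15 | Power, K = 15 |
|---|---|---|---|---|
| 1 cm | 2.54 | 0.88 | 2.55 | 0.87 |
| 2 cm | 2.65 | 0.85 | 2.69 | 0.84 |
| 3 cm | 2.83 | 0.80 | 2.92 | 0.78 |

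Power is for 3 cm at 15 per arm, unadjusted.

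**4. Chance imbalance.** This is the same cost as step 3 seen within a single trial, not a second one. Under simple allocation of 15 and 15, the number of pre-treated patients in one arm is hypergeometric. The probability that the arms differ by five or more is 0.035 for K = 8, 0.050 for K = 10 and 0.143 for K = 15. (For even K the difference is even, so this means six or more.) A difference of five moves the estimate by d × 5/15; with d = 2 this is 0.67 cm, or 0.67 / 3 = 22% of the target. Blocking within gender would reduce the probability. The Protocol gives no block size. Simulating K = 15 with two gender strata of equal expected size gives about 0.02 for blocks of 4 and 0.05 for blocks of 6.

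**5. Possible dilution.** Suppose the effect is 3 cm in untreated patients and e in pre-treated patients, with d = 0. The average effect is 3(1 − p) + ep. The variance in the capsaicin arm is 2.5² + p(1 − p)(3 − e)², in the placebo arm 2.5², and the SD used is the square root of their mean.
- e = 1.5: for K = 15, average 2.25 cm, SD 2.56, power 0.64. For K = 8, average 2.60 cm, SD 2.54, power 0.77.
- e = 0: for K = 15, average 1.50 cm, SD 2.72, power 0.31. For K = 8, average 2.20 cm, SD 2.67, power 0.59.

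Nothing in the documents says whether e differs from 3.

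**6. What a subgroup test could show.** With K = 15, each stratum has 7 or 8 patients per arm. Power for the full 3 cm within a stratum is 0.54 to 0.61. Power for an interaction as large as 3 cm against 0 is 0.35.

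**The case against.** A reader might infer that carry-over from the earlier antiemetic distorts the treatment effect. It does not. Carry-over can affect individual scores, but it precedes randomization and cancels in expectation, as step 2 shows.

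A reader might also infer that the trial now mixes two separate questions, capsaicin alone and capsaicin added to an antiemetic. The Protocol does not support so sharp a division. Conventional therapy was open to both arms throughout, so patients enrolled under the first rule could also have received an antiemetic before the 30-minute reading. The comparison was always capsaicin plus usual care against placebo plus usual care. What the change altered is who enters: later treatment does not undo selection on persisting nausea.

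Third, the change is disclosed and its stated reason is logistic. Nothing in the documents suggests that it followed from unblinded results.

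Finally, the precision loss is modest. The extra variance is already reflected in the confidence interval that the SAP promises, and the worst case in step 3 (0.78) is close to the 80% planned for 12 per group. The increase to 30 was meant in part to cover an imprecise effect size. All of this stands and limits the point to precision and reporting. It does not remove the case for using a baseline variable that should be available and costs one degree of freedom.

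**Conclusion.** The point holds as a matter of precision and interpretation; the validity of the randomized comparison is not in question. If 8 to 15 of 30 patients were pre-treated and the shift is 1 to 3 cm, unadjusted power at 15 per arm is 0.88 to 0.78 instead of 0.89. An imbalance large enough to move the estimate by 0.67 cm at a 2 cm shift is uncommon: 0.04 to 0.14 under simple allocation, less with blocking. Dilution could cost much more, but only if the effect is smaller in pre-treated patients, which remains a hypothesis. The share pre-treated, the shift and any difference in effect are all assumptions. The statement that nothing separates the two kinds of patient refers to the SAP text available, part of which was removed before review.

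**What to change.** 1. Report the number of patients with an ED antiemetic before randomization, by arm and by period before and after the change.
2. Add an estimate of the 30-minute VAS difference with 95% CI adjusted for prior ED antiemetic (yes/no). If outcome data have already been seen, label it a sensitivity analysis. The SAP's reference to one patient's missing scores and their imputation suggests that they have.
3. Show the treatment difference with 95% CI separately for patients with and without a prior ED antiemetic, labelled descriptive. Make no formal subgroup test, and set no rule that withholds the conclusion if the two estimates diverge: at 7 or 8 per arm, noise would decide.
4. State that the conclusion applies to this mixed population.
5. Reconcile the retained 24-hour outpatient exclusion with the admission of patients given an ED antiemetic, and give the reason for the difference.

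Changing the stratification is no longer possible, since the Protocol reports enrollment complete in July 2019.

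The cost is SAP wording and one table, provided that the treatment data entered in REDCap record antiemetics given before randomization. Adjustment spends one degree of freedom: about one percentage point of power if the variable proves unrelated to outcome, against recovery of most of the losses in step 3 if it is related. The stratum intervals will be wide.

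### Randomization was stratified by gender, but every analysis in the SAP is unadjusted, so the stratification factor is never used

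*Protocol*

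**What the plan says.** The Protocol, under Interventions, Randomization, and Blinding, says: "Randomization used 1:1 allocation and stratified by gender". Gender is the only stratification factor named.

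The Statistical Analysis Plan section of the SAP names two families of tests:

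- Continuous outcomes, including the primary 30-minute VAS: "student's t-test, or Mann-Whitney U test, as appropriate for unadjusted comparisons of continuous variables between treatment groups".
- Categorical outcomes: Chi-square or Fisher's exact test, again "for unadjusted comparisons of categorical outcomes between treatment groups".

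The SAP also commits to "report primary results with 95% confidence intervals (CI" and to two-tailed testing at 0.05. Nothing in the supplied text uses gender as a covariate or stratum, or says why it was left out.

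**The concern.** Stratified randomization makes the arms alike in gender mix. If gender predicts the outcome, that balance removes the between-gender part of the variance from the treatment difference. An ordinary two-sample t-test still counts that part in its error term. Its standard error is then larger than the true one, its interval covers more than 95%, and its p-values are too large on average.

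What is at stake is precision and correct coverage, not validity. The estimate is unbiased and the false-positive rate does not exceed 5%. The balance from stratification is also kept whichever analysis is used. But in a pilot with 30 planned patients the interval is a main product, and the data needed to sharpen it are already held.

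**Working it through.** **Inputs from the documents.** Difference 3 cm, SD 2.5 cm, two-sided alpha 0.05, 80% power, 12 per group calculated, 30 planned in total (SAP); 1:1 allocation stratified by gender (Protocol).

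**Assumptions.** 15 per arm; each arm has 8 patients of one gender and 7 of the other; normal outcomes; total within-arm SD 2.5 cm. The share of variance explained by gender (R²) is not in the documents, so it is varied over 0%, 5%, 10% and 20%.

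**Step 1: reproduce the plan's figure.** For a two-sample t-test with 12 per group, the noncentrality is 3 / (2.5 × √(2/12)) = 2.94 on 22 degrees of freedom, which gives 80.2% power. With 11 per group, power is 76.3%. So 12 per group is right, and it rests on an unadjusted t-test. With 15 per group, power is 88.7%.

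**Step 2: translate R² into a gender gap.** With 16 of 30 patients of one gender, p(1 − p) = (16/30)(14/30) = 0.249, and gap = √(R² × 6.25 / 0.249). This gives 1.1, 1.6 and 2.2 cm for R² of 5%, 10% and 20%.

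**Step 3: compare the true variance with what the t-test estimates.**

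- True variance of the difference: (2/15) × 6.25 × (1 − R²).
- Expected squared standard error from the t-test: (2/15) × 6.25 × (1 − R² + R² × 15/14).
- Ratio k = (1 − R²) / (1 − R² + R² × 15/14) = 0.947, 0.894 and 0.789.
- Approximate type I error: P(|t₂₈| > 2.048/√k). The cut-offs are 2.105, 2.167 and 2.306, giving 4.4%, 3.9% and 2.9%.

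**Step 4: simulation.** 200,000 trials per setting (simulation standard error below 0.1 point), t-test v linear model with treatment and gender:

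| R² | Gap (cm) | Type I error | Mean 95% CI width (cm) | Power at 3 cm |
|---|---|---|---|---|
| 0% | 0 | 5.0% v 5.0% | 3.71 v 3.71 | 88.6% v 88.6% |
| 5% | 1.1 | 4.5% v 5.1% | 3.71 v 3.62 | 89.2% v 90.2% |
| 10% | 1.6 | 3.8% v 4.9% | 3.72 v 3.52 | 89.7% v 91.6% |
| 20% | 2.2 | 2.9% v 5.0% | 3.73 v 3.32 | 90.8% v 94.3% |

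From unrounded widths, the interval is 2.6%, 5.4% and 11.1% narrower. The simulated type I errors agree with step 3.

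**Step 5: sensitivity.**

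- At 12 per arm (6 and 6), power at 3 cm is about 81% v 82%, 81% v 84% and 82% v 88% for R² of 5%, 10% and 20%.
- With a 10 and 5 gender mix per arm, the results are nearly the same (t-test type I error 4.4%, 3.9% and 2.8%).

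**Step 6: rank tests.** Mann-Whitney v gender-stratified van Elteren, 15 per arm, power at 3 cm: 87.0% v 85.4%, 87.5% v 87.3%, 88.0% v 88.9% and 88.8% v 92.1% for R² of 0%, 5%, 10% and 20%. At R² of 20%, type I error is 2.9% v 4.9%.

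**The case against.** The strongest reply is that the stated analysis is already valid. It holds type I error at or below 5%, the sample size was calculated for exactly this test, and 15 per group gives about 89% power without adjustment. No document links gender to nausea. For a gap of about 1 cm the gain is 0.7 to 1.0 power point and roughly 0.1 cm on an interval 3.7 cm wide. The 11% gain needs a 2.2 cm gap, about three quarters of the 3 cm effect used for planning. An adjusted estimate added now is also post hoc, and it gives readers a second version of the primary result. All of this stands, and it limits the point to a refinement.

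Two further objections stand in part:

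- **Balance within gender is assumed, since no block size is stated.** With permuted blocks of 4, 6 or 10 the figures hold closely. Without blocking within gender, the t-test's type I error is not lowered (4.9% to 5.1%), though the adjusted model still gains power. With a chance split of 9/6 in one arm and 7/8 in the other, the adjusted interval is still narrower at R² of 5% (3.65 v 3.71 cm). With no gender effect, adjustment there costs about 0.7 power point.
- **The stratified rank test is not free.** With no gender effect it loses 87.0 − 85.4 = 1.6 points.

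Neither removes the mismatch between design and analysis, and neither makes the linear model costly.

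**Conclusion.** The point holds, as a modest refinement. The trial stratifies by gender and no analysis in the supplied text uses it. If gender predicts the VAS, the t-test interval is too wide and the test is conservative: type I error is about 4.5% to 2.9%, and the interval is 2.6% to 11.1% wider than the adjusted one, as a share of its own width, for R² of 5% to 20%. If gender does not predict the VAS, there is no loss. These sizes rest on 15 per arm, SD 2.5 cm, normal outcomes, near-balance within gender and an assumed R². The planned sample size and the validity of the stated analysis are unaffected.

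**What to change.** Add a linear model with treatment and gender for the 30- and 60-minute VAS. Report the gender-adjusted difference and 95% interval beside the unadjusted result, which remains the SAP's stated analysis. If Mann-Whitney is the test used, add van Elteren's test stratified by gender, noting its small cost above.

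Label the adjusted results as not pre-specified. The Protocol reports that "Patients were enrolled between December 2017 and July 2019", and the SAP already describes observed data: "For one patient in the capsaicin group, the nausea VAS at 30 and 60 minutes was missing". Include gender in the multiple imputation model as well, so that imputation and analysis agree. For admission and rescue medication, a gender-stratified Cochran-Mantel-Haenszel test is the counterpart. Its strata would be small with 30 patients and its gain was not quantified here, so it is optional.

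The cost is one degree of freedom per VAS model, about 0.1 power point with balanced arms and no gender effect. No new data are needed, because gender was recorded for randomization.

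### Baseline nausea is recorded but no planned test adjusts for it; at 60 minutes a baseline-adjusted ANCOVA would be more precise if baseline correlates with outcome above about 0.2

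*Protocol*

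**What the plan says.** **Measurement.** Protocol, Methods and Measurements: "We measured the intensity of the patient's nausea upon randomization and at 30- and 60-minutes following application of study medication". Every randomized patient should therefore have a baseline reading on the same 0 to 10 cm scale.

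**Outcomes.** The primary outcome is the 30-minute VAS. For 60 minutes, the Outcomes section reads: "Secondary outcomes were the patient's reported nausea and percent change from baseline at 60 minutes". One reading is thus used in two forms, and neither has priority.

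**Analysis.** The SAP names "student's t-test, or Mann-Whitney U test, as appropriate for unadjusted comparisons of continuous variables between treatment groups" and adds: "A p-value <0.05 (two-tailed) was considered statistically significant for all tests". Neither document contains a baseline-adjusted model. Randomization is stratified by gender (Interventions, Randomization, and Blinding), but no stated analysis uses the stratum.

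**Entry.** Study Design and Setting excludes "those with resolution of nausea prior to randomization" but sets no lowest VAS. The mid-trial change "allowed enrollment of patients that received an antiemetic medication in the ED prior to randomization as long as nausea was still present".

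**Missing data.** "For one patient in the capsaicin group, the nausea VAS at 30 and 60 minutes was missing"; multiple imputation was used.

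**The concern.** Neither 60-minute form makes good use of the baseline reading. The raw score discards it. Percent change uses it as a divisor, so a patient who enters with a VAS of 1 cm can contribute an extreme ratio, and entry does not rule such patients out. ANCOVA uses the same reading without forming a ratio and gives a difference in centimetres.

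What is at stake is precision. With 30 planned patients the 60-minute interval is wide, and a covariate already in the database may narrow it. A narrower estimate would also help in planning a follow-on trial. The validity of the randomized comparison is not in question.

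**Working it through.** **Inputs from the documents.** Difference 3 cm, SD 2.5 cm, two-sided alpha 0.05, 12 per group for 80% power, 30 planned, 1:1 allocation (15 per arm). The 3 cm and 2.5 cm are stated for the 30-minute outcome; using them at 60 minutes is an assumption.

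**Inputs not in the documents.** The correlation r between baseline and 60-minute VAS, the baseline mean and SD, and the placebo mean at 60 minutes. These are varied below.

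**Step 1: the plan's own figure.** A two-sample t-test (noncentral t) has power 76.3% at 11 per group and 80.2% at 12. The stated 12 reproduces. At 15 per arm power is 88.7%.

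**Step 2: ANCOVA by formula.** Residual SD = 2.5 × √(1 − r²), inflated by √(1 + 1/(2n − 4)) for estimating the slope, with 2n − 3 degrees of freedom. For n = 15 the inflation is √(1 + 1/26) = 1.019, with 27 degrees of freedom.

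Break-even with the raw test: (1 − r²)(1 + 1/26) = 1, so r² = 1/27 and r = 0.19; in round terms, 0.2.

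Raw 95% half-width: 2.048 × 2.5 × √(2/15) = 1.87 cm. ANCOVA half-width: 2.052 × 2.5 × √(1 − r²) × 1.019 × √(2/15).

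| r | ANCOVA power | Raw power | ANCOVA half-width | Raw half-width |
|---|---|---|---|---|
| 0 | 87.5% | 88.7% | 1.91 cm | 1.87 cm |
| 0.2 | 88.7% | 88.7% | 1.87 cm | 1.87 cm |
| 0.3 | 90.3% | 88.7% | 1.82 cm | 1.87 cm |
| 0.6 | 97.3% | 88.7% | 1.53 cm | 1.87 cm |

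**Step 3: simulation on the bounded scale, with percent change.** Bivariate normal readings, 15 per arm, 20,000 trials per row, placebo 60-minute mean 5 cm, SD 2.5 cm, difference 3 cm. These are values before clipping. Readings are then clipped to 0–10 cm, with baseline held at or above 0.5 cm so that the ratio exists. After clipping, the difference is about 2.7 cm and the SDs about 2.4 and 2.1 cm, so half-widths are smaller than in Step 2.

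| Baseline mean/SD (cm) | r | Raw t | ANCOVA | % change, t | % change, Mann-Whitney |
|---|---|---|---|---|---|
| 8/1.5 | 0.3 | 88% | 89% | 90% | 88% |
| 8/1.5 | 0.6 | 88% | 96% | 94% | 93% |
| 7/2 | 0.3 | 88% | 89% | 86% | 87% |
| 7/2 | 0.6 | 88% | 96% | 96% | 95% |
| 6/2.5 | 0.3 | 88% | 90% | 64–65% | 83% |
| 6/2.5 | 0.6 | 88% | 97% | 89% | 95% |

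Half-width, ANCOVA against raw: 1.62 v 1.66 cm at r = 0.3 (1.62/1.66 = 0.98, 2% narrower) and 1.38 v 1.66 cm at r = 0.6 (0.83, 17% narrower). At r = 0, ANCOVA power is 87% against 88%.

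**Step 4: a smaller effect.** At 2.5 cm before clipping, raw power is 74% to 75%. ANCOVA gives about 77% at r = 0.3 and 89% at r = 0.6, and 73% at r = 0. The pattern is the same.

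The simulated ANCOVA contains treatment and baseline only. The gender stratum would cost one further degree of freedom (27 to 26) and was not simulated.

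**The case against.** The strongest reply is that this is an optimisation and not a defect. The unadjusted tests are valid under randomization, the outcome is secondary, and the trial is a pilot. That stands, and it sets the severity.

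The gain is also conditional. Background treatment chosen by the treating physician, and antiemetics given before randomization, could both weaken the link between baseline and 60-minute nausea. At r = 0.2 nothing is gained, and at r = 0.3 the gain is 1 to 2 points. That also stands.

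A reader might infer more, in four ways that the documents do not support:

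- *That ANCOVA would certainly do better.* The correlation is not given, and below about 0.2 it would do slightly worse.
- *That percent change is a poor measure here.* The large loss needs low, variable baselines and is greatest with a t-test on skewed ratios; the SAP allows Mann-Whitney instead. At 8/1.5 cm and r = 0.3, percent change matches ANCOVA. Low baselines are permitted but not shown to have occurred.
- *That two tests of one reading seriously inflate error.* Under the null, simulation gives at least one false positive in 6.3% to 8.5% of trials, which carries little weight for secondary outcomes of a pilot.
- *That no interval would be given at 60 minutes.* The SAP says it will "report primary results with 95% confidence intervals (CI"; this may mean the main results generally.

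**Conclusion.** The concern holds as a minor point of efficiency. The plan records baseline VAS and adjusts for it nowhere. With 15 per arm, adjustment helps the 60-minute comparison if r is above about 0.2. At the plan's 3 cm and SD 2.5 cm, the gain over the raw test is about 2 points of power at r = 0.3 and about 8 at r = 0.6; the cost is 1 to 2 points at r = 0. Against percent change, a clear advantage appears only with low, variable baselines.

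These sizes rest on an assumed correlation, assumed baseline distributions, and the 30-minute planning values carried to 60 minutes. The argument for adjustment applies equally to the 30-minute primary outcome. Nothing here shows bias, an invalid test or an inadequate sample size.

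**What to change.** **In this trial's report.** Add one ANCOVA of 60-minute VAS on treatment, baseline VAS and the gender stratum. Fit it in each imputed data set, pool the results, and report an adjusted difference in cm with a 95% interval. Give the same model for the 30-minute VAS as a supportive analysis.

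The text describes completed enrolment and a known missing patient, so the ANCOVA can only be post hoc. Label it so and make no significance claim from it. Keep the raw and percent-change comparisons, with their p-values, as the planned secondary results. This matters because a third p-value would raise the chance of at least one false positive from 6.3%–8.5% to 7.4%–9.5% in the null simulations.

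**In a follow-on trial.** Prespecify the ANCOVA as the single 60-minute test and report percent change descriptively.

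**Cost.** One extra model and a short paragraph; no new data. The downsides are its post hoc status here and a small loss of power if baseline is not predictive. In a follow-on trial, relative reduction would also no longer be tested.
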